4.2 EXCLUSION CRITERIA

Subjects meeting any of the following criteria are excluded from participation in this study:

1. Use of a prohibited therapy or not willing to wash-out drugs as mentioned in the prohibited therapies section (Section 6.2);
2. History (in the past year) or presence of drug or alcohol abuse;
3. Suicide attempt in the past 3 years;
4. Previous or current history of a malignant tumor (except basal cell carcinoma);
5. Active liver disease or jaundice, or out-of-range values of alanine aminotransferase (ALT) and aspartate aminotransferase (AST); or total bilirubin >1.3 times the upper limit of normal (ULN); or creatinine >1.5 times the ULN; or estimated glomerular filtration rate (eGFR) using the Modification of Diet in Renal Disease (MDRD) formula <60 mL/min/1.73 m² at screening;
6. Medical condition or chronic disease (including history of neurological [including cognitive], hepatic, renal, cardiovascular, gastrointestinal, pulmonary [e.g., moderate asthma], or endocrine disease) or malignancy that could confound interpretation of the study outcome, as judged by the Investigator;
7. Any psychological disorder according to the criteria indicated in the Diagnostics and Statistical Manual of Mental Disorders (DSM, 4th edition) within one year prior to screening. Such disorders include but are not limited to current major depression, alcohol (more than 3 glasses of wine, beer, or equivalent/day) or substance abuse/dependence;
8. Judged by the Investigator to be unsuited to participate in the study, based on findings observed during physical examination, vital sign assessment, or 12-lead ECG;
9. History of severe allergy, hypersensitivity, or intolerance to drugs in general, including the study drug and any of its excipients;
10. Presence or sequelae of gastrointestinal, liver, kidney or other conditions known to interfere with the ADME mechanisms of drugs, as judged by the Investigator;
11. Concurrent participation in another interventional study (or participation within 3 months prior to screening in this study);
12. History of poor compliance in clinical studies;
13. Unable or unwilling to complete the study procedures;
14. Subject is the Investigator or any sub-investigator, research assistant, pharmacist, study coordinator, or other staff or relative thereof who is directly involved in the conduct of the study.

5. **TREATMENT(S)**

Manufacturing, packaging, and labeling of the study drug, ESN364, will be done under the responsibility of the Sponsor.

The ESN364 and placebo capsules are manufactured under current Good Manufacturing Practice (GMP), as required by the current Good Clinical Practice (GCP), at Pharmavize N.V. (Mariakerke, Belgium).

5.1 PHYSICAL DESCRIPTION OF THE STUDY DRUG

The Investigational Medicinal Product (IMP), ESN364 capsules, is being developed as an immediate-release hard gelatin capsule for oral administration in an active dosage strength range of 2.25 mg to 180 mg. In this clinical study, only the 90 mg strength will be tested. The qualitative composition of the ESN364 capsules is provided in [Table 1](#).

Table 1: Qualitative Composition of ESN364 Hard Gelatin Capsules

Component	Function
ESN364	Active pharmaceutical ingredient
Starch, pregelatinized	Filler
Croscarmellose sodium	Disintegrant
Silicon dioxide	Glidant
Magnesium stearate	Lubricant
Coni snap size 0 white opaque hard gelatin capsule (opaque white cap/opaque white body)	Capsule shell

5.2 OTHER MEDICATION ADMINISTERED IN THE STUDY

Placebo is supplied as hard gelatin capsules that match the IMP. Placebo capsules contain the same excipients as the IMP. The capsule shells used for manufacturing of placebo capsules are identical to the capsule shells used for manufacturing of ESN364 capsules.

5.3 PACKAGING AND LABELING

The packaging and labeling of study drugs will be in accordance with applicable local regulatory requirements.

The ESN364 and placebo capsules will be packaged in high-density polyethylene (HDPE) bottles with polypropylene closure. Each bottle will contain 68 capsules of ESN364 or placebo. A patient kit containing 3 bottles of study drug will be foreseen for each subject.

Labels will be printed in the local language of the countries where the study takes place in accordance with applicable local regulations and will contain the following:

- EudraCT number
- Protocol number
- Medication number
- Visit number
- Date of manufacture and/or expiration date

- Batch number
- Storage conditions
- Contents
- The statements 'Keep out of reach and sight of children', 'For oral route only', 'For clinical trial use only'
- Sponsor (or sponsor representative) name

5.4 STORAGE AND DRUG ACCOUNTABILITY

The Investigator (or his/her designee) is responsible for the safe storage of all study drugs assigned to the clinical site, in a locked, secure storage facility with access limited to those individuals authorized to dispense the study drugs, and maintained within the appropriate ranges of temperature. All study drugs must be stored as specified at delivery and in the original packaging. Instructions for the subjects, regarding the storage and handling of the study drugs, will also be provided to the clinical sites.

ESN364 must be stored at ambient conditions (15-30°C or 59-86°F), should not be exposed to freezing temperatures, and should be protected from light during storage at the clinical site.

Daily temperature logging of the study drug storage room at the clinical site should be performed. In case a deviation in storage conditions should occur, the site must not further dispense the affected study drug and notify the Clinical Research Associate (CRA) or Pharmavize N.V.

For the available stability data of ESN364 capsules and placebo, please refer to the Investigational Medicinal Product Dossier (IMPD).

The Investigator is responsible for ensuring that all study drugs received at the clinical site are inventoried and accounted for throughout the study. As misallocations of study drugs may have a detrimental effect on subjects' safety and/or the study drugs' efficacy and are a potential source of bias, utmost care should be taken to correctly dispense the study drugs as assigned by the randomization system.

Study drugs will be dispensed to the subjects at Visits 2, 3, and 4 (one bottle containing 68 capsules at every visit). Study drugs should be dispensed under the supervision of the Investigator, a qualified member of the clinical staff, or the hospital/clinic pharmacist. The Investigator must maintain accurate records demonstrating date and amount of study drugs supplied to whom and by who. Study drugs will be supplied only to subjects participating in the study.

The site monitor will periodically check the supplies of study drugs held by the Investigator or pharmacist to ensure accountability and appropriate storage conditions of all study drugs used.

Subjects must be instructed to return all unused study drugs at every visit. A record of any returned study drugs will be kept for each subject. Returned study drugs must not be relabeled or dispensed again, not even to the same subject.

Unused study drugs and study drugs returned by the subject (if applicable) must be available for verification by the site monitor during on-site monitoring visits. Any

discrepancies between returned and expected returned study drugs should be explained and documented.

After the last visit of the last subject in the study (Last Patient Last Visit [LPLV]), any unused study drug will be returned to the Sponsor.

5.5 RANDOMIZATION

In total 80 subjects are planned to be randomized to one of 2 treatment arms in a 1:1 ratio: ESN364 90 mg b.i.d. (40 subjects) or placebo (40 subjects).

Randomization will be based on a computer-generated randomization schedule prepared by the Secure Data Office (SDO) Department of SGS Life Science Services using SAS® software (SAS Institute Inc., Cary, NC, USA) prior to the start of the study. The randomization will be balanced using randomly permuted blocks across the treatment arms.

The randomization list will be uploaded into the randomization module of the Electronic Data Capture (EDC) system. Based on this randomization list, the study drugs will be packaged and labeled. Medication numbers will be preprinted on the study drug labels.

At the clinical site, through the randomization module of the EDC system, subjects will automatically be assigned a randomization number as soon as they qualify for the study.

5.6 BLINDING

Blinding will be achieved by the double-dummy method with placebo identical in smell, taste, and appearance.

The randomization list will be retained by SDO until the end of the study (database lock). A copy will be sent in a sealed envelope to the bioanalytical laboratory responsible for plasma drug determination before the start of the study.

The randomization list will not be available to the Investigator or other employees of the clinical site, subjects, monitors, or personnel of SGS Life Science Services departments other than SDO before unblinding of the data, unless in case of emergency. The Sponsor's clinical team will also be blinded during the study as they will not have direct access to the randomization list. The Clinical Research Organization (CRO) performing data management and statistical activities will receive a copy of the randomization list at database lock.

The study drug administered to a subject can be identified by the Interactive Web Response System (IWRS). IWRS will allow rapid access to the treatment allocation codes when relevant for site or CRO personnel. However, codes should only be broken if it is considered as mandatory because of a life-threatening situation for management of medical treatment. In such case, the date at which breaking of the code occurs, the person who breaks the code, and the reason why the code is broken will need to be documented in the subject's file. Site personnel should inform the Medical Monitor (SGS Life Science Services) immediately. If the Investigator accidentally breaks the code, the Medical Monitor must be also informed as soon as possible.

If the code is broken by the Investigator or by someone of his/her clinical staff, the subject must be withdrawn from the study and must be followed as appropriate. If the

code is broken by the Sponsor or designee for safety reporting purposes the subject may remain in the study.

At the time of the interim analysis, which will be conducted on the primary endpoint, DEXA parameters and safety data once the first 16 subjects will have completed 12 weeks of treatment and the follow-up visit (or have discontinued earlier), the interim analysis subjects' treatment arm will be unblinded. All other subjects will remain blinded.

5.7 DOSE AND ADMINISTRATION

A rationale for the dose of study drug selected in this study is provided in Section [3.2](#).

Subjects will be randomly, sequentially, and in a blinded fashion assigned to one of 2 treatments arms (i.e., ESN364 90 mg b.i.d. [total daily dose of 180 mg] or placebo) in a 1:1 ratio according to the randomization schedule. An overview of the treatment in each of the treatment arms is provided in [Table 2](#).

Table 2: Treatment Overview

Treatment Arm	Number of Subjects	Treatment
ESN364 90 mg b.i.d.	40	oral dose of 90 mg ESN364 b.i.d. for 12 weeks
Placebo	40	oral dose of placebo b.i.d. for 12 weeks

All visits need to be planned in the morning, fasted (for unbiased glucose, insulin, and C-peptide determination). Visit 2 should be planned to allow for first intake of study drugs at the clinical site, between 7:00 and 10:00 AM. For each subject, all visits during the treatment period subsequent to Visit 2 should be planned at the same time of the day, in the morning.

Study drugs will be dispensed to the subjects at Visits 2, 3, and 4 (one bottle containing 68 capsules at every visit).

The first intake of study drug (Day 1; Visit 2) will be done at the clinical site (between 7:00 and 10:00 AM), under the supervision of the clinical staff. Study drug intake will be done with a glass of tap water at room temperature. Also on other days of visits, the morning dose of study drug will be taken at the clinical site, under the supervision of the clinical staff, after collection of predose blood samples. Subjects will be instructed not to consume food/fluids for at least 10 hours before their visit to the clinical site (except water intake until one hour before). On all other days throughout the treatment period, subjects will be asked to take their morning dose of study drug at home, around the same time of the day (preferably between 7:00 and 10:00 AM). Morning intake at home may be done together with a light meal.

All evening doses of study drug will be taken at home (preferably between 7:00 and 10:00 PM).

Subjects need to record all home study drug intakes in the Electronic Patient Reported Outcome (ePRO) diary.

In case a subject accidentally misses a scheduled dose of the study drug and this is noticed within 12 hours of the time of scheduled intake, the missed dose should be taken

as soon as possible, with or without food. The subject may then continue her usual dosing schedule. In case a subject accidentally misses a scheduled dose of the study drug and this is noticed more than 12 hours after the time of scheduled intake, the missed dose should be skipped and the subject should simply resume her usual dosing schedule.

Any deviation from the treatment regimen defined in the protocol must be documented in the electronic Case Report Form (eCRF).

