6. Medical condition or chronic disease (including history of neurological [including cognitive], hepatic, renal, cardiovascular, gastrointestinal, pulmonary [e.g., moderate asthma], or endocrine disease) or malignancy that could confound interpretation of the study outcome;
7. Any psychological disorder according to the criteria indicated in the Diagnostics and Statistical Manual of Mental Disorders (DSM, 4th edition) within one year prior to screening. Such disorders include but are not limited to current major depression, alcohol (more than 3 glasses of wine, beer, or equivalent/day) or substance abuse/dependence;
8. Judged by the Investigator to be unsuited to participate in the study, based on findings observed during physical examination, vital sign assessment, or 12-lead ECG;
9. History of severe allergy, hypersensitivity, or intolerance to drugs in general, including the study drug and any of its excipients;

10. Presence or sequelae of gastrointestinal, liver, kidney or other conditions known to interfere with the absorption, distribution, metabolism, or excretion (ADME) mechanisms of drugs, as judged by the Investigator;
11. Concurrent participation in another interventional study (or participation within 3 months prior to screening in this study);
12. History of poor compliance in clinical studies;
13. Unable or unwilling to complete the study procedures;
14. Subject is the Investigator or any sub-investigator, research assistant, pharmacist, study coordinator, or other staff or relative thereof, who is directly involved in the conduct of the study.

Test Product, Dose, Mode of Administration:

ESN364 capsules to be taken orally b.i.d. with a glass of tap water at room temperature. The dose level of ESN364 that will be investigated is 90 mg b.i.d. (total daily dose of 180 mg)

Reference Product, Dose, Mode of Administration:

Matching placebo capsules to be taken orally b.i.d. with a glass of tap water at room temperature.

Study/Treatment Duration:

The total duration of involvement for each subject, screening through study exit, will be at most 19 weeks: the study will consist of a screening period (screening is to be performed within 4 weeks prior to the first intake of study drug, with a minimum of 7 days to allow for baseline data collection of Hot Flash Score and Hot Flash Frequency) and a 12-week double-blind treatment period (Weeks 1-12). A follow-up visit will be scheduled 2-3 weeks after the last study drug intake.

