1.3 CLINICAL STUDIES

To date, the development program of ESN364 includes only one recently completed study, conducted in 65 subjects. A dose range between 3 and 180 mg as single dose in fasted and fed conditions, and up to 21 days of dosing in a multiple dose setting was tested. Both sexes were included in this study. Male healthy volunteers have been dosed up to 10 consecutive days and healthy female subjects of childbearing potential have been dosed up to 21 consecutive days in accordance with their menstrual cycle. The highest dose in both multiple dose parts was 180 mg q.d.

The results of the Phase I study demonstrated that administration of single and multiple ascending doses up to 180 mg of ESN364 were safe and well tolerated.

No deaths occurred during the study. The majority of reported treatment-emergent adverse events (TEAEs) were mild to moderate in severity. A severe TEAE was reported in 1 (7.1%) subject in the placebo treatment group. One serious adverse event (SAE) (foot fracture) was reported in 1 (5.9%) subject during the follow-up period and led to withdrawal of the subject from the study.

The most frequently reported TEAEs (i.e., those reported in >2 subjects per treatment group) following multiple ascending dosing for 21 days in healthy female subjects were abdominal pain in 3 (50.0%) subjects each in the placebo and 180 mg ESN364 treatment group, nausea in 3 (50.0%) subjects in the 20 mg ESN364 treatment group, headache in 3 (50.0%) and 4 (66.7%) subjects in the 60 mg and 180 mg ESN364 treatment groups,

respectively, and dry skin in 3 (50.0%) subjects in the 180 mg ESN364 treatment group. Nausea and headache were only reported in the 20 mg, 60 mg, and 180 mg ESN364 treatment groups and not in the placebo treatment group.

All subjects had recovered or were recovering from the TEAEs by the end of the study.

All treatment-emergent laboratory abnormalities (worst-case) were observed in at most 2 subjects per treatment group, except for some isolated elevated abnormally high potassium levels and isolated low levels of total bilirubin. None of the laboratory abnormalities were considered to be of clinical relevance, and as a consequence none of the laboratory abnormalities were reported as adverse event (AE).

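### The missed-dose rule in Section 5.7 has a 12-hour catch-up window equal to the nominal b.i.d. interval and no minimum gap, so it permits two 90 mg doses together and, after some missed evening doses, 270 mg in one calendar day against a stated 180 mg

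*Protocol*

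**What the plan says.** Section 5.7 of the protocol describes the arms as "ESN364 90 mg b.i.d. [total daily dose of 180 mg] or placebo", and Section 5.1 adds that "In this clinical study, only the 90 mg strength will be tested", so each intake is one capsule. Home morning doses are to be taken "around the same time of the day (preferably between 7:00 and 10:00 AM"), and for the other intake "All evening doses of study drug will be taken at home (preferably between 7:00 and 10:00 PM"). On visit days the morning dose is taken at the site after the predose blood samples.

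For a dose missed by accident, Section 5.7 has two branches:

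- If the omission is "noticed within 12 hours of the time of scheduled intake, the missed dose should be taken" promptly, regardless of meals, and the subject is then free to go back to her normal schedule.
- If it is noticed later than 12 hours after the scheduled time, the dose is skipped and the normal schedule resumes.

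The section gives no minimum gap between a late dose and the next one, no bar on taking two doses together, and no exception for visit mornings. Section 7.1.2 describes the regimen as q.d., although the same paragraph goes on to mention evening and morning doses.

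**The concern.** A catch-up window as long as the dosing interval does not separate a late dose from the next one. On a 12-hour schedule the skip branch starts only once the next dose is already due. A subject who follows the text exactly can therefore take two capsules together, and can pass the daily amount that the same section states.

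Three things are at stake:

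- **Dosing clarity for outpatients over 12 weeks.** Section 1.3 says of the completed Phase I study that "The highest dose in both multiple dose parts was 180 mg q.d". It also reports that exposure in women rose more than in proportion to dose at that level.
- **Visibility.** Because the late capsule is shifted rather than added, a capsule count looks like full compliance. Only intake times can show the pattern.
- **Predose samples at Visits 3 to 5.** A missed evening dose remembered on a visit morning is to be taken promptly, while the morning dose is held until blood has been drawn. The text does not say which instruction governs the late capsule.

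**Working it through.** **Inputs (protocol).** Dose per intake 90 mg and 180 mg a day (Section 5.7); morning window 07:00–10:00 and evening window 19:00–22:00 (Section 5.7); take the missed dose if noticed at 12 h or less, otherwise skip (Section 5.7).

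**Stated figure reproduced.** 2 × 90 mg = 180 mg a day.

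**Dosing interval from the windows.**
- Same clock time morning and evening: 12 h.
- Shortest: 10:00 to 19:00, or 22:00 to 07:00, = 9 h.
- Longest: 07:00 to 22:00, or 19:00 to 10:00, = 15 h.

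**Catch-up window minus interval.**
- 12 − 12 = 0 h: the window closes exactly when the next dose is due.
- 12 − 9 = +3 h: the window runs 3 h past the next scheduled dose.
- 12 − 15 = −3 h: the window closes 3 h before the next dose.

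**Intake under the rule, 08:00/20:00 schedule.**

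| Missed dose | Noticed | Highest calendar-day total | Shortest gap between intakes |
|---|---|---|---|
| Evening | 0.5–3 h late (before midnight) | 180 mg | 11.5 down to 9 h |
| Evening | 4–11 h late | 270 mg | 8 down to 1 h |
| Evening | 12 h late (08:00) | 90 + 90 + 90 = 270 mg | 0 h |
| Morning | 0.5–12 h late | 180 mg | 11.5 down to 0 h |
| Either | 12.5 h late | 180 mg (skipped) | 12 h |

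The ratio is 270 / 180 = 1.5. The day of the missed evening dose has only its morning 90 mg, so the two-day total is 90 + 270 = 360 mg = 2 × 180 mg, as planned.

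**Other schedules.** For 07:00/19:00, 10:00/22:00, 07:00/22:00 and 10:00/19:00 the pattern is the same. A total of 270 mg in a calendar day arises only from a missed evening dose taken at or after midnight. A missed morning dose never produces it, because 12 h after 07:00–10:00 is 19:00–22:00 on the same day. On 07:00/22:00 a missed evening dose noticed at 9 h coincides with the morning dose. On 10:00/19:00 a missed evening dose never comes closer than 3 h to the next dose, but a missed morning dose noticed at 9 h coincides with the evening dose.

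**Choice of measure.** A rolling 24-hour total reaches 270 mg after a delay of only half an hour, so it does not separate harmless lateness from doubling up. The calendar-day total and the shortest gap are more informative.

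**Visit mornings.** Section 5.7 holds the morning dose until after predose sampling but says nothing about a late evening dose. Section 1.3 gives a median time to peak in women of 3 to 4 hours, so a capsule taken on waking could put a sample labelled predose on the rise towards peak.

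**The case against.** The strongest reply is that this is a worst case about timing and not an overdose. Much of that stands.

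- The late capsule is shifted and the two-day total does not rise.
- No passage calls 180 mg a daily maximum; it describes the regimen.
- The permission to continue the normal schedule is worded as an option.
- Two capsules together equal the 180 mg single intake that Section 1.3 reports as given once daily for up to 21 days in women and well tolerated.
- As a rough check, assume first-order decline at the longest mean half-life in Section 1.3, 7.06 h, and ignore any residue from doses before the missed one. The fraction left after 12 h is 0.5^(12/7.06) = 0.31. Then 0.31 × 180 ≈ 55 mg, and adding the next 90 mg gives about 145 mg, less than one 180 mg intake. The more-than-proportional exposure in women makes this only indicative.
- Compliance under Section 5.8 uses ePRO entries as well as capsule counts, so the pattern can be detected.
- A subject who missed her evening dose has no ordinary trough whether she catches up or skips. Sampling times relative to intake are listed (Sections 9.1.2 and 9.1.3), and PK is exploratory.

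What does not fall away is that the section sets a 180 mg day and also gives an instruction that, followed exactly, can produce a 270 mg day. That is more than any daily amount reported in Section 1.3. The visit-morning order of events is also left open.

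A reader might go further and infer that subjects will routinely double up, that a dose forgotten overnight is the usual case, or that the 12-hour limit was carried over from a once-daily regimen. The documents give no frequency of missed doses and no origin for the limit, so none of these is supported.

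**Conclusion.** The point holds as an internal inconsistency in an operative dosing instruction. The rule permits two 90 mg doses at or near the same time. After a missed evening dose noticed after midnight and within 12 hours, it permits 270 mg in one calendar day, 150% of the stated 180 mg. It does not produce this in general: evening doses caught up before midnight and all missed morning doses leave the day at 180 mg, and the two-day total remains 360 mg.

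This rests on reading the rule literally and on subjects keeping a fixed schedule within the stated windows. The number of affected subjects cannot be estimated from the protocol. The documents do not show that the resulting exposure is unsafe, or that the primary endpoint is affected. The effect on predose PK and PD values is limited to subjects who miss the evening dose before a visit. It is worth correcting because it concerns what subjects are told to take and the remedy is small.

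**What to change.** In Section 5.7, the sponsor should reconcile the missed-dose rule with the b.i.d. interval and the 180 mg daily dose stated there. The text should make clear whether two doses close together, or more than 180 mg in a calendar day, are intended to be possible. It should also say how a missed evening dose is handled on a visit morning before predose sampling. Section 7.1.2 should be reconciled with Section 5.7 on q.d. versus b.i.d. What the clinical rule should be is the sponsor's decision.

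For data review, check ePRO intake entries for closely spaced intakes. On visit days combine them with the site record, because only home intakes go into the diary.

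Cost: one paragraph in Section 5.7, a wording correction in Section 7.1.2, and matching changes to any subject-facing dosing instructions that repeat the rule. No new procedures or data collection are needed.
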